SOP	Standard Operating Procedure
UP	Unanticipated Problem
US	United States

STATEMENT OF COMPLIANCE

The trial will be conducted in accordance with the ICH E6, the Code of Federal Regulations on the Protection of Human Subjects (45 CFR Part 46). The Principal Investigator will assure that no deviation from, or changes to the protocol will take place without prior agreement from the sponsor and documented approval from the Institutional Review Board, except where necessary to eliminate an immediate hazard(s) to the trial participants. All personnel involved in the conduct of this study have completed Human Subjects Protection Training.

I agree to ensure that all staff members involved in the conduct of this study are informed of their obligation to meet the above commitments.

Principal Investigator: [name]
Print/Type Name

Signed: _____ Date: _____

STUDY SUMMARY

Title: A Single-Arm, Open-Label Phase 2 Pilot Study of Vyxeos (CPX-351) in Adults with Relapsed or Refractory Acute Lymphoblastic Leukemia.

Objectives:

Primary Objective:

- 1) To estimate the complete response rate following treatment with CPX-351

Important Secondary Objectives:

- 1) To evaluate the safety and tolerability of CPX-351
- 2) To estimate minimal residual disease burden following treatment with CPX-351
- 3) To estimate the progression free survival (PFS) following treatment CPX-351
- 4) To estimate the overall survival (OS) following treatment with CPX-351

Endpoint

Primary Endpoint:

- 1) Complete remission rate

Important Secondary Endpoints:

- 1) To evaluate the safety and tolerability of CPX-351
- 2) Minimal Residual Disease Burden
- 3) PFS
- 4) OS

Population:

Patients ≥ 18 years old with relapsed acute lymphoblastic leukemia (ALL) who are registered at the Moffitt Cancer Center.

Phase:

2, pilot

Number of Sites enrolling participants:

1

Description of Study

Agent :

- 1) Induction: Vyxeos (CPX-351), 100 units/m² days 1, 3, & 5
- 2) Consolidation: Vyxeos (CPX-351) 65 units/m² days 1 & 3 (up to 3 cycles)

Study Duration:

[figure not shown]
24 months

Participant Duration:

30 months

SCHEMATIC OF STUDY DESIGN

Induction	CPX-351 100 u/m ² 90 minute infusion days 1,3,5
Consolidation Per section 7.3.2.11	CPX-351 65 u/m ² 90 minute infusion days 1,3 (administered 35-75 days after start of induction) for up to 3 cycles.

2 INTRODUCTION: BACKGROUND INFORMATION AND SCIENTIFIC RATIONALE

2.1 BACKGROUND INFORMATION

Outcomes are poor among adults with relapsed and refractory ALL, with most chemotherapy regimens demonstrating a CR rate of ~40%, coupled with a median EFS of ~6mo. (ref 1-10). To this end, several

novel therapies have emerged, including blinatumomab (CR/CRi rate 43%, med OS 7.7mo), inotuzumab ozagomycin (CR/CRi rate 80.7%, med OS 7.7mo), and liposomal vincristine (CR/CRi rate 20%, 6mo OS 35%). (ref 11-13). While these therapies have advanced the management of relapsed ALL, relapse and shortened life expectancy remain the expectation for most patients.

Chemotherapy resistance has been related in part to the overexpression of cell proteins implicated in drug transmembrane transport, such as PGP and LRP. (ref 14-18). Attempts to intensify therapy by increasing anthracycline dose or with the use of novel anthracycline derivatives have not significantly improved outcome. (ref 8-9,19). More recently, trials using liposomal daunorubicin in conjunction with high dose cytarabine demonstrated improved clinical efficacy (CR 80%, 12mo OS 39%). Notably, in cells from those with increased expression of multi-drug resistant proteins (72% of patients), the in vitro retention of liposomal daunorubicin and subsequent apoptosis were both significantly higher, when compared with free daunorubicin. (ref 18) Recent work further suggests molar ratio of cytarabine:daunorubicin, in addition to drug uptake, may be important in yielding therapeutic response. (ref 20-21)

CPX-351 (or Vyxeos) is a liposomal formulation of cytarabine and daunorubicin at a fixed molar ratio. A randomized study of CPX-351 (vs non-liposomal cytarabine and daunorubicin) in high risk acute myeloid leukemias demonstrated a significant benefit in complete remission rates (47.7% vs 33.3%) and median overall survival (9.56 vs. 5.95 months), culminating in FDA approval August 2017.

Preclinical and early clinical data using primary ALL cell samples suggests that this benefit may extend to those with lymphoblastic leukemias. Specifically, "high sensitivity" to CPX-351 was observed in 20% of samples. (ref 22). This was further corroborated with xenograft modeling using samples derived from pediatric patients with relapsed ALL, wherein response was estimated via ORM modeling to be 100%, with response in 4 of 5 mouse groups suggestive of CR. Notably, activity was also observed in a Philadelphia chromosome positive patient derived xenograft. (ref 23) Finally, CPX-351 was also tested clinically during phase 1 testing in 3 patients with ALL, with one showing subsequent CR. (ref 24)

Based on these data, the author believes there is rationale for further study of this approach in relapsed and refractory ALL.

2.2 RATIONALE

Remission rates vary considerably depending on population studies (children vs adults), relapsed vs refractory status, and timing of salvage (first relapse vs beyond first relapse) making it difficult to extrapolate baseline rate. If focusing specifically on 2 trials that used an induction composed of cytarabine (3gm/m² x5d) and idarubicin (40mg/m² on d3), complete remission rates are approximately 40% (38-44%, total n=54). (ref 4-5). Alternatively, a more recent phase 3 trial of inotuzumab vs standard of care in patients in first or second relapse shows a composite CR rate in the standard of care arm (Cytarabine+Mitoxantrone, high dose Cytarabine, and Fludarabine, Cytarabine, and GCSF, total n=109) of 29%. (ref 13). Given these data, it is determined that a baseline CR rate of 35% is likely to estimate activity with a standard salvage regimen.

Data using liposomal anthracyclines among those with relapsed ALL, including FLAD (Fludarabine, Cytarabine, Liposomal Daunorubicin) and Cytarabine+Liposomal Daunorubicin, have shown an improvement in CR rates, at 65% and 80%, respectively. (ref 18,28) Together these data suggest a CR rate of 65% should be attainable using CPX-351.

However, at this stage, a phase 2 pilot trial is proposed to explore response rates among 10 patients with ALL. Should sufficient activity be observed, consideration may be made in consultation with Jazz

Pharmaceuticals, to increase the budget to increase accrual to formally test our hypothesis, possibly in a multicenter setting.

Safety will be monitored as per standard routine, accounting for adverse events using CTCAE v. 5.0. Myelotoxicity is anticipated, in addition to associated infections. Frequency of these events will be monitored for comparison with historical rates, referencing against historical regimens noted above. Adverse events of special interest include bone marrow aplasia (hypocellular marrow without adequate count recovery >42 days from start of therapy), and *symptomatic* heart failure (accompanied by a decrease in the ejection fraction >10% from baseline greater than 42 days from start of therapy).

2.3 POTENTIAL RISKS AND BENEFITS

2.3.1 KNOWN POTENTIAL RISKS

The table below summarizes adverse reactions obtained directly from the Investigator Brochure Version 13.0. The table includes pooled data from five clinical trials of 375 patients with AML. The frequency is referenced using the following MedDRA scale:

- Very common: $\geq 1/10$ ($\geq 10\%$);
- Common (frequent): $\geq 1/100$ and $< 1/10$ ($\geq 1\%$ and $< 10\%$);
- Uncommon (infrequent): $\geq 1/1,000$ and $< 1/100$ ($\geq 0.1\%$ and $< 1\%$);
- Rare: $\geq 1/10,000$ and $< 1/1,000$ ($\geq 0.01\%$ and $< 0.1\%$);
- Very rare: $< 1/10,000$ ($< 0.01\%$), including isolated reports.

System Organ Class	All AEs/Frequency	Grade 3-5 AEs/Frequency
Blood and lymphatic system disorders	Very Common Febrile neutropenia Common Neutropenia Thrombocytopenia Anemia	Very Common Febrile neutropenia Common Neutropenia Thrombocytopenia Anemia
Cardiac disorders	Very Common Cardiotoxicity Arrhythmia Chest pain	Very Common Cardiotoxicity Common Arrhythmia Chest pain
Eye disorders	Very Common Visual impairment	Uncommon Visual impairment
Gastrointestinal disorders	Very Common Mucositis Abdominal pain Constipation Decreased appetite Diarrhea/colitis Nausea Vomiting Common Dyspepsia	Common Mucositis Abdominal pain Constipation Decreased appetite Diarrhea/colitis Nausea Uncommon Vomiting Dyspepsia
General disorders and administration site conditions	Very Common Edema Pyrexia Fatigue Chills	Very Common Fatigue Common Edema Pyrexia Uncommon Chills
Immune system disorders	Very Common Hypersensitivity	Common Hypersensitivity
Infections and infestations	Very Common Infection	Very Common Infection
Metabolism and nutrition disorders	Common Tumor lysis syndrome	Common Tumor lysis syndrome

Musculoskeletal and tissue disorders	Very Common Musculoskeletal pain	Common Musculoskeletal pain
Nervous system disorders	Very Common Headache Dizziness	Common Headache Uncommon Dizziness
Psychiatric disorders	Very Common Delirium Sleep disorders Anxiety	Common Delirium Uncommon Sleep disorders
Renal and urinary disorders	Very Common Renal insufficiency	Common Renal insufficiency
Respiratory, thoracic and mediastinal disorders	Very Common Dyspnea Pleural effusion Cough	Very Common Dyspnea Uncommon Pleural effusion
Skin and subcutaneous disorders	Very Common Pruritis Hyperhidrosis Common Alopecia Night sweats Uncommon Palmar-plantar erythrodysesthesia syndrome	Uncommon Hyperhidrosis
Vascular disorders	Very Common Hemorrhage Hypertension Hypotension	Very Common Hemorrhage Common Hypertension Hypotension

2.3.2 KNOWN POTENTIAL BENEFITS

Initial work with primary ALL cell samples suggested “high sensitivity” to CPX-351 in 20% of samples. (ref 22). This was further corroborated with xenograft modeling using samples derived from pediatric patients with relapsed ALL. Specifically, response was estimated via ORM modeling to be 100%, with response 4 of 5 mouse groups suggestive of CR. Notably, activity was also observed in a Philadelphia chromosome positive patient derived xenograft. (ref 23) Finally, CPX-351 was also tested clinically during phase 1 testing in 3 patients with ALL, with one showing subsequent CR. (ref 24) Based on these data, there is reason to believe there could be benefit to subjects with relapsed and refractory ALL.

To date we have treated 7 patients with CPX-351. We have seen CR in two patients and PR in 3 other evaluable patients following induction (ORR 83%). Relevant grade 3-5 SAE’s to date include: bleeding, veno-occlusive disease of the liver, and fungal pneumonia.

3 OBJECTIVES AND PURPOSE

Primary Objective:

To estimate the complete response rate following treatment with CPX-351. Complete remission will be evaluated by bone marrow biopsy at day 28 of therapy in all patients with medullary disease receiving at least one full cycle of CPX-351. For patients with extramedullary disease, CT or PET/CT will be used for response. Cheson criteria (2003) will be used to evaluate remission status, specifically complete remission (CR), complete remission with incomplete hematologic recovery (CRi/CRh), partial response (PR), and aplasia.

Important Secondary Objectives:

Additional clinical endpoints will include

- 1) To evaluate safety and tolerability of CPX-351 using CTCAE 5.0.
- 2) Minimal residual disease assessment (MRD) by 10 color flow cytometry and next generation sequencing (NGS) by Clonoseq (for Philadelphia negative leukemia) or PCR for BCR-ABL (for Philadelphia positive leukemia).
- 3) Progression Free Survival as defined by Cheson Criteria, namely progression, failure to respond, or death, as assessed from time of first treatment.
- 4) Overall Survival as defined by Cheson Criteria, namely death due to any cause as assessed from time of first treatment.

4 STUDY DESIGN AND ENDPOINTS

4.1 DESCRIPTION OF THE STUDY DESIGN

This is an open label, single arm, single center, phase 2 pilot study of Vyxeos induction & consolidation in relapsed and refractory ALL.

4.2 STUDY ENDPOINTS

4.2.1 PRIMARY ENDPOINT

- We will measure remission rate at day 28 to address the primary endpoint of complete remission (with or without complete hematologic recovery), as defined by Cheson Criteria (ref 27). For those with extramedullary disease, Lugano criteria will be used to assess response (ref 32). This is a standard assessment of drug efficacy for phase 2 clinical trial design in acute leukemias, as response correlates closely with progression free- and overall survival (PFS and OS).

4.2.2 SECONDARY ENDPOINTS

Secondary Endpoints will include

- 1) Evaluation of safety of CPX-351 using CTCAE 5.0.
- 2) Minimal residual disease assessment (MRD) by 10 color flow cytometry and next generation sequencing (NGS) by Clonoseq (for Philadelphia negative leukemia) or PCR for BCR-ABL (for Philadelphia positive leukemia) at day 28. Using a threshold of 0.01% leukemic cells, MRD provides a better estimate leukemic cell sensitivity to therapy, and correlates with both PFS and OS.
- 3) Progression Free Survival as defined by Cheson and Lugano Criteria (ref 27 and 32), namely progression, failure to respond, or death, as assessed from time of first treatment. The 12 month progression free survival rate with standard chemotherapeutic approaches in relapsed ALL is estimated at 10%. PFS is a standard estimate that accounts for response rate, response duration, and mortality to estimate therapeutic benefit in clinical trials.
- 4) Overall Survival as defined by Cheson and Lugano Criteria (ref 27 and 32), namely death due to any cause as assessed from time of first treatment. The 12 month overall survival for those with standard chemotherapeutic approaches in relapsed ALL estimated at 20%. Overall survival is a standard criteria for assessing therapeutic benefit in clinical trials.

4.2.3 EXPLORATORY ENDPOINTS

Exploratory Endpoints will include:

- 1) An exploration of the activity of CPX-351 ex vivo using live image capture in a reconstituted tumor micro-environment (EVOS system) as a potential biomarker for response.

- 2) An assessment of apoptotic threshold as a measure of tumor cell fitness (dynamic BH3 profiling). These data may additionally support combinatorial approaches using clinical inhibitors of apoptosis.
- 3) An assessment of the T-cell repertoire using multi-parameter flow, and tumor/stromal PDL1 expression. These data will similarly be used to support potential future combinatorial strategies.

5 STUDY ENROLLMENT AND WITHDRAWAL

5.1 PARTICIPANT INCLUSION CRITERIA

Patients must meet all of the following criteria to be eligible for study entry:

1. Be willing and able to provide written informed consent/assent for the trial.
2. Be ≥ 18 years of age on day of signing informed consent.
3. Able to adhere to the study visit schedule and other protocol requirements.
4. Pathologically confirmed B- or T-cell acute lymphoblastic or mixed phenotype acute leukemia, with $\geq 5\%$ peripheral blood or bone marrow lymphoblasts and/or extramedullary disease $>1 \times 1 \text{ cm}$.
5. Relapsed or refractory acute lymphoblastic leukemia after at least 1 prior cycle of therapy. Patients with Philadelphia chromosome positive disease must have failed at least two prior tyrosine kinase inhibitors.
6. Eastern Cooperative Oncology Group (ECOG) performance status 0-1.
7. Cardiac ejection fraction $\geq 50\%$ by echocardiography or MUGA.
8. Must be at least 2 weeks out from any prior systemic chemotherapy, blinatumumab, radiation, and/or other investigational agents, and have recovered to grade 1 from any toxicity related to prior therapy. Glucocorticoids are permitted up to 1 day prior to the first dose.
9. Serum bilirubin and creatinine $\leq 1.5 \times$ upper limit of normal (ULN). AST and ALT must be $\leq 3 \times$ ULN, unless there is suspected liver involvement.
10. Females of childbearing potential (FCBP) must have a negative serum pregnancy test at screening. A FCBP is considered when a sexually mature female: 1) has not undergone a hysterectomy or bilateral oophorectomy; or 2) has not been naturally postmenopausal for at least 12 consecutive months.
11. A FCBP must agree to use of two methods of highly effective contraception, be surgically sterile, or abstain from heterosexual activity for the course of the study through 30 days after the last dose of study treatment.
12. Male subjects must agree to use an adequate method of contraception starting with the first dose of study therapy through 30 days after the last dose of study therapy. Men must agree to not donate sperm during and after the study

5.2 PARTICIPANT EXCLUSION CRITERIA

Any of the following is a criterion for exclusion from the study:

1. Clinical evidence of active central nervous system (CNS) leukemia.
2. Any major surgery or radiation therapy within four weeks.
3. Any active infection requiring systemic therapy, including HIV, Hepatitis B, and/or Hepatitis C.
4. Has a history or current evidence of any condition, therapy, or laboratory abnormality that might confound the results of the trial, interfere with the subject's participation for the full duration of the trial, or is not in the best interest of the subject to participate, in the opinion of the treating investigator (including but not limited to severe graft-versus-host disease, unstable angina, pulmonary hypertension, active/prior veno-occlusive disease of the liver, or severe CHF (NYHA III-IV).
5. Patients with active (uncontrolled, metastatic) second malignancies are excluded.
6. Is pregnant or breastfeeding, or expecting to conceive or father children within the projected duration of the trial, starting with the screening visit through 30 after the last dose of trial treatment.
7. Hypersensitivity to cytarabine, daunorubicin, or liposomal products.
8. History of Wilson's disease or other copper-metabolism disorder.
9. Patients with prior cumulative anthracycline exposure of greater than 368 mg/m² daunorubicin (or equivalent).

5.3 STRATEGIES FOR RECRUITMENT AND RETENTION

Recruitment of the 10 participants for this trial will occur from new or established patients treated at the Hematology Clinic at Moffitt Cancer Center. Screen failure is anticipated to be less than 10%. The target accrual is expected to be reached in 24 months. All faculty members in the Lymphoma Section will be sub-investigators on the trial. They will be trained on the trial design, study agents, and eligibility criteria. This will equip each investigator to discuss the trial with potential participants as appropriate. The trial will be listed on the Moffitt Cancer Center website (www.moffitt.org) for the availability of local physicians to refer patients who could be eligible for the trial.

All investigators will be made aware of the emphasis to enroll women and minorities. The design of the trial and eligibility criteria are not restrictive relative to women and minorities. According to the National Cancer Institute Surveillance, Epidemiology, and End Results Program, there are approximately 6000 new cases of ALL per year, of which nearly half will occur among those over age 20 years. (ref. 29) In a currently enrolling Moffitt trial (MCC18329) for patients with ALL, 50% of participants were young adults (age 18-39), 25% were female, and 100% were Hispanic/Portuguese. The sex, ethnicity, and race of each participant on this trial will be captured in the Oncore electronic data base for reporting purposes.

The multi-modal aspect of this disease will require knowledge of the barriers to recruitment and retention present to young adults, older adults, and those who may be Hispanic. The young adult population can be challenging to interest in trial participation. The article by Pearce (ref. 30) provides understanding of communication strategies, the need of young adults to feel autonomous, and the importance young adults place on being treated in a specialist care setting to facilitate trial participation.

The article could be utilized as a resource for trial staff. Once consented, the young adult participant will have contact with the research nurse frequently during trial participation to maintain continuity and provide support, which Pearce describes as a way to impact retention.

Potential participants will be assessed prior to screening for any perceived barriers related to the clinical trial process. Referrals will be made to a social worker, supportive care services, financial services, or the research nurse to address barriers prior to consent.

5.4 PARTICIPANT WITHDRAWAL OR TERMINATION

5.4.1 REASONS FOR WITHDRAWAL OR TERMINATION

Subjects may withdraw consent at any time for any reason or be dropped from the trial at the discretion of the investigator should any untoward effect occur that may jeopardize participant safety. In addition, a subject may be withdrawn by the investigator if enrollment into the trial is inappropriate, the trial plan is violated, or for administrative and/or other safety reasons.

A subject must be discontinued from the trial for any of the following reasons:

- The subject or legal representative (such as a parent or legal guardian) withdraws consent
- Unacceptable adverse events
- Intercurrent illness that prevents further administration of treatment
- Investigator's decision to withdraw the subject
- The subject has a confirmed positive serum pregnancy test
- Noncompliance with trial treatment or procedure requirements
- The subject is lost to follow-up
- Administrative reasons

The End of Treatment and Follow-up visit procedures are listed in the Schedule of Events and Section 7.3 (Visit Requirements). After the end of treatment, each subject will be followed for 30 days for adverse event monitoring. Subjects who discontinue for reasons other than progressive disease will have post-treatment follow-up for disease status and toxicity up to 30 days. Follow-up rules will apply unless participant initiates a non-study cancer treatment, withdraws consent, or becomes lost to follow-up (unsuccessful attempts to contact for 3 months). After documented disease progression, each subject will be followed 12 months for overall survival until death, withdrawal of consent, or the end of the study, whichever occurs first.

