7.1.13 Bone Marrow Biopsy

A bone marrow biopsy will be performed at screening and at day 28. If determined the subject has extramedullary disease (as permitted in inclusion criterion #4), biopsy of the involved area will be the method by which correlative samples will be obtained, provided this can be safely obtained. If extramedullary disease is confirmed and the bone marrow biopsy is shown to be negative prior to trial participation, no bone marrow biopsy will be required at day 28. If subject discontinues treatment early or progression of disease is suspected, a bone marrow biopsy will be done at the discretion of the investigator. During follow-up, bone marrow biopsies will be performed per investigator discretion.

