7.3.3 FOLLOW-UP

After the end of treatment assessment, all subjects will be followed with procedures and physical examinations per standard of care.

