7.3.5 EARLY TERMINATION VISIT

If a subject terminates study participation for any reason prior to completion of the protocol treatment plan, any subsequent procedures or evaluations will be per physician discretion as part of standard of care. Evaluation of AEs will continue as outlined in Section 7.1.9.

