10.4.3 ANALYSIS OF THE SECONDARY ENDPOINT(S)

- Minimal Residual Disease (MRD) will be studied as a dichotomous endpoint using a cutoff of 1×10^{-4} cells/transcripts as the lower limit for residual leukemia, and presented as the percentage of patients reaching this landmark as their best response. MRD assessment will be obtained with each bone marrow biopsy assessment, as described below.
- Progression Free Survival and Overall Survival will be reported as per Cheson and Lugano Criteria, and analyzed using a standard Kaplan-Meier approach. Patients will undergo bone marrow biopsy evaluation after each cycle of therapy per standard of care to facilitated assessment. Patients achieving CR/CRi at the end of consolidation with marrow involvement will have follow-up bone marrow biopsy evaluation every 3 months in the first year following their last cycle of therapy, and every 6 months in the subsequent 2 years following their last cycle. Patients who remain in remission greater than 3 years from their last cycle of therapy will have bone marrow biopsy evaluation performed as needed. Patients without marrow involvement will have follow-up imaging (CT or PET/CT) every 3 months in the first year following their last cycle of therapy, and every 6 months in the subsequent 2 years following their last cycle. Patients progressing to allogeneic transplant following therapy will be censored at the time of conditioning.
- Safety will be continually assessed during the course of induction and consolidation cycles. Safety assessment will continue at a minimum of every 3 months for those who do not progress to allogeneic transplant or alternative therapy.

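### Sections 5.4.1, 7.1.13 and 7.3.5 do not match the PFS assessment schedule in 10.4.3, so a marrow-disease responder who stops early has no stated disease follow-up beyond 30 days and no stated censoring rule

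*Combined protocol and SAP*

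**What the plan says.** **Section 5.4.1** (withdrawal): "Subjects who discontinue for reasons other than progressive disease will have post-treatment follow-up for disease status and toxicity up to 30 days". These follow-up rules end sooner if the patient starts non-study cancer treatment, withdraws consent or is lost. The only longer follow-up in that section is for survival: "After documented disease progression, each subject will be followed 12 months for overall survival until death". It supplies no disease status to a patient who has not progressed.

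**Section 7.1.13** (marrow): "During follow-up, bone marrow biopsies will be performed per investigator discretion".

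**Section 7.3.3** (follow-up): after the end-of-treatment assessment "all subjects will be followed with procedures and physical examinations per standard of care". No interval is given.

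**Section 7.3.5** (early termination): "any subsequent procedures or evaluations will be per physician discretion as part of standard of care".

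**Section 7.3.7** (schedule of events): the follow-up column carries one general mark and no disease assessment.

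**Section 10.4.3** (secondary analysis): PFS is analysed by Kaplan-Meier. Patients with marrow involvement who are in CR/CRi at the end of consolidation "will have follow-up bone marrow biopsy evaluation every 3 months in the first year following their last cycle of therapy", then every 6 months for the next 2 years. Patients without marrow involvement have CT or PET/CT at the same intervals, with no condition about completing consolidation. The one stated censoring rule is at conditioning for allogeneic transplant.

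**Section 4.2.2** counts progression, failure to respond and death as PFS events from first treatment, and cites a 12-month PFS of 10% for standard chemotherapy.

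**The concern.** PFS needs one rule for when disease is assessed and one for when a patient is censored. Here the rule depends on which section staff open. Failure to respond is already an event, so patients still at risk after the day 28 assessment are essentially responders. Those among them who stop for toxicity or intercurrent illness, or by investigator decision, are the ones whose disease follow-up 5.4.1 ends at 30 days.

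Two things are at stake. The first is information: with about 10 patients, each responder whose disease status is not collected weakens the later part of the curve. The second is possible informative censoring: if patients who stop early relapse sooner than those who stay on treatment, censoring them a month after the last dose raises the Kaplan-Meier estimate. Assessment driven by symptoms also dates relapse differently from assessment at fixed visits.

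**Working it through.** **1. Which rule applies to whom**

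| Patient without a PFS event | 5.4.1 | 7.1.13 / 7.3.5 | 10.4.3 |
|---|---|---|---|
| Completes consolidation in CR/CRi, marrow disease | not a discontinuation | marrow at discretion (7.1.13) | marrow at fixed times for 36 months |
| No marrow involvement | 30 days if stopped early | discretion if stopped early (7.3.5) | imaging at fixed times for 36 months |
| Marrow disease, responder, stops before the end of consolidation | 30 days | discretion | not covered by the marrow schedule |

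The first row is a conflict between discretion and a fixed schedule. The third row is a gap: no section sets disease assessment after 30 days or a censoring date. Such a patient has completed induction and so belongs to the efficacy set in 10.3. No section says which rule governs.

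**2. Duration.** Section 10.4.3 runs 12 + 24 = 36 months from the last cycle. The study summary gives a participant duration of 30 months, which is shorter even before treatment time is added.

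**3. The plan's own figures.** The documents state no event count or power for PFS. The only design calculation is the illustrative Simon row in 10.4.2. With 35% and 65% response, more than 3 of 10 to continue and more than 9 of 19 to succeed, exact binomial sums give PET 0.514, average N 14.38, alpha 0.084 and beta 0.095. All match. That row concerns CR/CRi and has no bearing on follow-up.

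**4. What a 30-day window captures (early stoppers only).** Assume a constant relapse hazard λ from the end of treatment. The share of first-year relapses seen within 30 days is (1 − exp(−λ × 30/30.4375)) / (1 − exp(−12λ)).

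- Median 6 months: 0.108 / 0.750 = 14%.
- 12-month rate of 10% event-free: 0.172 / 0.900 = 19%.
- Median 12 months: 0.055 / 0.500 = 11%.

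So 81% to 89% of first-year relapses in this group would fall after the window. The documents give no relapse rate after stopping; these hazards are assumptions.

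**5. Effect on 12-month PFS.** Assumptions: response R of 35% or 65% (the plan's two rates); non-response counted as an event at day 28; median time to relapse 8 months from day 28, so λ = ln 2 / 8 = 0.0866; a fraction f of responders (30% or 50%) stop at a time s spread evenly over 0.15 to 4 months after day 28; relapse hazard multiplied by h after stopping; censoring 1 month after stopping. With L = 12 − 28/30.4375 = 11.08 months:

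PFS with full follow-up = R × [(1 − f) exp(−λL) + f × mean of exp(−λs − hλ(L − s))].

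For R = 0.65, f = 0.5, h = 2: exp(−0.0866 × 11.08) = 0.383. At the mean s of 2.075 the second term is exp(−0.0866 × (22.16 − 2.075)) = 0.176. Then 0.65 × (0.5 × 0.383 + 0.5 × 0.176) = 18.2%. The large-sample Kaplan-Meier value with 30-day censoring, by numerical integration of the hazard among those still under observation, is 23.6%.

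| R | f | h | Full follow-up | 30-day censoring | Difference, points |
|---|---|---|---|---|---|
| 65% | 50% | 1 | 24.9% | 24.9% | 0 |
| 65% | 50% | 2 | 18.2% | 23.6% | 5.4 |
| 65% | 50% | 3 | 15.1% | 22.5% | 7.4 |
| 35% | 30% | 1 | 13.4% | 13.4% | 0 |
| 35% | 30% | 1.5 | 12.1% | 13.2% | 1.1 |

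Over all combinations with h from 1.5 to 3 the rise is 1.1 to 7.4 points. At h = 1 there is no bias, but information is lost. With R = 0.65 and f = 0.5, the expected number observed event-free at 12 months falls from 10 × 0.65 × 0.383 = 2.5 to half of that, 1.2.

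**6. Scale against chance.** At 18.2% with 10 patients the standard error is √(0.182 × 0.818 / 10) = 12.2 points. The exact 95% interval for 2 of 10 is 2.5% to 55.6%.

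**The case against.** The strongest case on the other side is that few patients are affected and nothing is decided on PFS. Completers in CR/CRi have not discontinued and keep the 10.4.3 schedule; patients without marrow involvement have an imaging schedule there. Some early stoppers would leave PFS observation anyway, through non-study therapy or transplant conditioning. Section 5.4.2 promises efforts to keep contact and allows clinic visits to be tracked, and 7.3.3 follows all subjects under standard of care. The 30-day sentence also comes after a list of reasons for leaving the trial, some of which, such as withdrawn consent, make longer follow-up impossible. All endpoints are called exploratory (10.2, 10.4.11), and expansion turns on CR/CRi in 4 of 10. The largest modelled shift is below one standard error.

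Most of this stands and limits the size of the point. It does not remove the gap: permission to track visits is not an assessment schedule, 5.4.2 ties it to patients who remain at the centre, and neither 5.4.2 nor 7.3.3 gives a censoring date. The conflict between 7.1.13 and 10.4.3 for completers is also untouched.

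A reader might infer that the 30-day rule removes every patient still at risk for PFS. It does not, for the reasons just given. A reader might also infer that relapses in early stoppers would never be recorded. Routine-care follow-up could capture some; the documents simply do not require it.

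**Conclusion.** The sections contradict one another on disease follow-up, and this rests on the text alone. Early-stopping responders with marrow disease have no stated disease follow-up beyond 30 days and no stated PFS censoring rule; completers have a discretionary rule and a fixed one.

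The sure consequence is lost PFS information if 5.4.1 is followed as written. It would be tempting to conclude that 12-month PFS will be overstated by several points. The documents do not support that: the rise of about 1 to 7 points depends on an assumed hazard ratio of 1.5 to 3 after stopping, an assumed 8-month median and an assumed 30% to 50% stopping early, and it is zero if stopping is uninformative. With an exploratory endpoint and 10 patients this is a modest flaw. It is worth correcting because the results may be used to design an expansion or a later study, and because correction is cheap.

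**What to change.** - **5.4.1:** confine the 30-day period to toxicity. State that disease status is collected, whatever the reason for stopping treatment, until a PFS event, withdrawal of consent, loss to follow-up, non-study anticancer therapy, transplant conditioning or end of study.
- **10.4.3:** make the marrow schedule refer to the end of study treatment instead of the end of consolidation. For early stoppers, take disease status from routine-care assessments at the 10.4.3 timepoints, without requiring additional biopsies. State that PFS is censored at the last disease assessment in patients without an event.
- **7.1.13, 7.3.3, 7.3.5 and the table in 7.3.7:** cross-refer to 10.4.3.
- **Study summary:** reconcile the 30-month participant duration with the 36 months after the last cycle in 10.4.3.

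The cost is an amendment of wording and somewhat longer data collection for a few patients. Existing stops for consent, other therapy and transplant are kept, and no treatment rule changes.
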